## 7.6 Multiple Testing

A Hochberg procedure will be used to test the primary endpoints. Therefore, if the two-sided p-value for the estimate of time to hospital discharge is below 0.05 and the two-sided p-value for the estimate of time to recovery is below 0.05 the null hypotheses for both endpoints will be rejected. Otherwise, if the smallest of the two-sided p-values is below 0.025 only the null hypothesis associated with the smallest p-value will be rejected. In any other circumstance neither null hypothesis will be rejected.

The first key secondary endpoint will be formally tested using a two-sided alpha of 0.05 only if both primary endpoints are statistically significant. The second and third key secondary endpoints will be formally tested, in sequence, using a two-sided alpha of 0.05 only if all prior hypothesis tests are statistically significant.

## 8 Summary of Study Data

In general, continuous variables will be summarised through descriptive statistics, including the number of subjects, mean, standard deviation, median, minimum and maximum. Categorical variables will be summarised as frequencies and percentages. All summary tables will be structured with a column for each treatment in the order (Placebo, SNG001) and will be annotated with the total population size relevant to that table/treatment, including any missing observations. A total column, including all subjects within the analysis population will be included for study population tables only.

All available and relevant study data will be listed. All safety and study drug exposure data will be listed using the Safety population, PK concentrations and parameters will be listed using the PK population, immunogenicity results will be listed using the Immunogenicity population and all other data will be listed using the ITT population.

### 8.1 Subject Disposition

The number and percentage of subjects belonging to the following categories will be presented for the ITT population:

- ITT analysis population
- PP analysis population

## Statistical Analysis Plan (RotW)

Final v1.0, 08FEB2022

SG018

- Safety analysis population (summarised under actual treatment arm).
- Treatment status
  - Was not treated
  - Completed treatment
  - Discontinued treatment
  - Principal reason for premature treatment discontinuation.
- Study status
  - Completed study
  - Ongoing (in treatment phase, in short term follow-up [Day 15 – Day 35], In long term follow-up [after Day 35] – all categories to be included for the purposes of DSMC meetings and the interim analysis, just an ‘Ongoing – after Day 35’ category will be included for the primary analysis and to be removed completely for the final analysis).
  - Discontinued from the study
    - At any time
    - Day 1 – Day 14
    - Day 15 – Day 35
    - Day 36 – Day 90
    - Principal reason for premature study withdrawal.

Study discontinuation will be plotted by treatment using mosaic plots for the patients discontinued based on the above defined visit periods.

## 8.2 Protocol Deviations

Important protocol deviations will be summarised for the ITT population. The number and percentage of patients with at least one important protocol deviation will be presented as well as the number and percentage of patients with at least one protocol deviation within each protocol deviation category and subcategory, overall and by country and site.

## 8.3 Demographic and Baseline Variables

The following demographic and baseline information will be summarised for the ITT population. Data collected at the Day 0/ Day 1 visit will be used, unless otherwise indicated below.

- Age
- Sex
- Race
- Ethnic origin
- Care home residence (yes, no)
- Height, weight and BMI at screening.
- Presence of selected co-morbidities (hypertension, cardiovascular disease (excluding hypertension), diabetes, a chronic lung condition or cancer).
- Number of distinct co-morbidities (0, 1, 2, 3+).
- Smoking status (never smoked, former smoker, current tobacco user, current e-cig user).
- Duration of symptoms at baseline.

The summary of demographic and baseline information will be repeated for each of the subgroups defined in [Section 7.2](#). The number and percentage of patients within each subgroup will also be summarised.

A summary of oxygen use at randomisation will also be presented. Summary statistics will be presented for the baseline percentage FiO2, the baseline percentage oxygen saturation and the baseline S/F ratio.

#### 8.4 Medical History

Medical history will be coded using the version 23 of the Medical Dictionary for Regulatory Activities (MedDRA).

Medical history will be summarised for the ITT population by System Organ Class (SOC) and Preferred Term (PT). Summary tables will contain the number and percentage of patients. A patient who has multiple conditions in the same SOC or with the same PT will be counted only once in the patient counts. Medical history summaries will be sorted by the internationally agreed SOC order ([Appendix III](#)) and decreasing frequency of PT within SOC in the total column.

SARS-CoV-2 infection history at screening will be summarised for the ITT population. The number and percentage of patients experiencing each symptom of COVID-19 on admission to hospital will be displayed. In addition, the number and percentage of patients with each COVID-19 variant will be presented, where data are available.

The number and percentage of patients with comorbidities will be summarised by the comorbidity groups defined in [Section 7.2](#) and preferred term. Preferred terms falling under each comorbidity group will be identified by a blinded medical review of the study data.

#### 8.5 Medications

Medications will be coded according to the 2009 version of the World Health Organisation Drug Dictionary (WHODD) combined with the online 2020 version.

Medications will be defined as prior or concomitant in the hospital setting and prior, concomitant or post study treatment in the home setting. Prior and concomitant medications will be summarised for the ITT population by Anatomical Therapeutic Chemical (ATC) class level 3 and preferred drug name, where;

- ‘Prior’ medications are medications which started and stopped prior to the first dose of study drug.
- ‘Concomitant’ medications are medications which started prior to, on or after the first dose of study drug and up to 24 hours after the last dose of study drug and ended on or after the date of first dose of study drug or were ongoing at the end of the study.
- ‘Post study treatment’ medications will be defined as medications which were started more than 24 hours after the last dose of study treatment.

See [Section 7.3.3](#) for handling of partial dates for medications. In cases where it is not possible to define a medication as prior or concomitant the medication will be classified by the worst case; i.e. concomitant.

## Statistical Analysis Plan (RotW)

Final v1.0, 08FEB2022

SG018

Concomitant and post study treatment medications which are used for direct treatment of COVID-19 will be summarised, including the number and percentage of subjects receiving such treatment, broken down by treatment name. Medications used for treatment of COVID-19 will be identified by a blinded medical review of the study data.

COVID-19 vaccinations prior to study enrolment will be summarised, including the number and percentage of vaccinated subjects, the type of vaccine received, whether a single dose or double dose vaccine was received, whether the same vaccine was received for both doses and the time since each vaccination dose. Post randomisation COVID-19 vaccinations will also be summarised, including the number and percentage of non-vaccinated and vaccinated patients as well as the patients with the first dose pre-randomisation and second dose in follow-up period.

### 8.6 Treatment Compliance

Percentage treatment compliance will be summarised for the Safety population.

Treatment compliance is calculated as total number of received doses/ total number of scheduled doses x 100, where the total number of scheduled doses only includes doses prior to study withdrawal.

Percentage treatment compliance will be summarised through descriptive statistics and the number and percentage of patients with < 80%, 80% - <100% and 100% compliance will be presented.

Treatment compliance will also be summarised as the number and percentage of patients that missed dose due to:

- OSCI score of 5 or above
- Other reasons

The number of patients who received partially administered doses will also be summarised alongside the reason for partial administration.

### 8.7 Treatment Exposure

The duration of exposure and number of doses administered will be summarised for the Safety population. The duration of exposure is calculated as the number of days between first dose and last dose (inclusive), regardless of any missed doses. The number of doses administered will be summarised in the form of cumulative frequencies showing the number and percentage of patients receiving  $\geq 1$  dose,  $\geq 2$  doses,  $\geq 3$  doses etc., up to 14 doses. The number of doses missed will also be summarised. In addition, the number and percentage of patients fulfilling the study drug exposure criteria for the PP population (i.e. patients who receive at least two doses in the first 3 days) will be summarised.

## 9 Efficacy Analyses

All efficacy analyses and summaries described in this section will use the ITT population. Some efficacy analyses will be repeated for other populations and for the subgroups defined in [Section 7.2](#) as per table 7 below.

**Table 7: Planned efficacy analyses**

Planned Analysis	ITT	PP	Subgroups of the ITT
Cox proportional hazards analysis of time to hospital discharge	X	X	X 
Cox proportional hazards analysis of time to recovery	X	X	X 
Kaplan Meier analysis of time to hospital discharge	X	X	X 
Kaplan Meier analysis of time to recovery	X	X	X 
Logistic regression analysis of severe disease or death within 35 days of first dose	X	X	X 
Logistic regression analysis of intubation or death within 35 days of first dose	X	X	X 
Logistic regression analysis of death within 35 days of first dose	X	X	
Logistic regression analysis of recovery at days 7, 14, 21 and 28	X	X	
Logistic regression analysis of hospital discharge at days 7, 14, 21 and 28	X	X	
Proportional odds analysis of improvement on the OSCI scale at days 7, 14, 21 and 28	X	X	X
Mixed model for repeated measures (MMRM) analysis of BCSS total score	X		
MMRM analysis for breathlessness and cough scores	X	X	X

Analysis will only be performed if sufficient events occur within the analysed population.

## 9.1 Primary Efficacy Endpoints

### 9.1.1 Time to Hospital Discharge

#### 9.1.1.1 Primary Estimand

The primary estimand will be the hazard ratio of SNG001 versus placebo for the time to hospital discharge of patients in the ITT population. Intercurrent events will be handled as per table 8.

**Table 8: Intercurrent events and policies for the primary estimand of time to hospital discharge**

Intercurrent event	Policy
Death	Composite variable: Patients who die on or prior to Day 28 will have time to hospital discharge right censored at 28 days (the maximum time to discharge).
Premature treatment discontinuation and missed doses	Treatment policy: The time to hospital discharge will be used regardless of treatment discontinuation and the number of missed doses.
Withdrawal from study following hospital discharge	Hypothetical: The time to hospital discharge will be used regardless of study withdrawal where discharge was sustained for 7 days. Otherwise, patients will be censored at the last date known to be hospitalised for patients who withdrew during the 7 day rebound period. This approach has been proposed because discontinuation during the rebound period is expected to be due to lack of interest/lack

	of motivation/lack of time to continue participating in the study rather than relapse.
Withdrawal from study prior to hospital discharge	While-on-study: Time to hospital discharge will be right censored at the time of withdrawal from the study or at 28 days, whichever occurs first. The evaluation period for this endpoint is 28 days, therefore estimating the time to hospital discharge after Day 28 would not be appropriate. Premature study withdrawal is expected to be independent to the treatment effect, therefore a censoring approach in this scenario is considered appropriate. However, this assumption will be tested by appropriate sensitivity analyses.
Other protocol deviations and concomitant medications affecting efficacy	Treatment policy: Time to hospital discharge will be used regardless of any concomitant medication use or protocol deviations.

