8.1 Sample Size Determination

Success will be determined if at least one of the primary endpoints is declared statistically significant by the primary analysis. A sample size of 610 patients in total using a 1:1 randomisation ratio (305 patients per treatment arm) has been chosen to provide at least 90% power to detect a hazard ratio of 1.45 in time to hospital discharge and a hazard ratio of 1.7 in time to recovery and at least 95% power to declare statistical significance on at least one of the primary endpoints. This sample size has been calculated using a global 2-sided alpha level of 0.05 and adjusting for the Hochberg procedure to allow for multiple comparisons. This also allows for an interim analysis to assess futility after the first 300 randomised patients have completed the Day 35 visit or have withdrawn from the study.

The sample size calculation assumes a hospital discharge rate in the placebo treatment arm of 70% at Day 28, a recovery rate in the placebo treatment arm of 30% at Day 28 and a dropout rate of 25% over the 28-day evaluation period with time to dropout exponentially distributed.

By their definition the two primary endpoints are naturally correlated. This correlation has been estimated from prior study data and has also been considered in the sample size calculation.

More details regarding the sample size calculation used for the study will be provided in the SAP.

The key secondary endpoint of progression to severe disease or death within the 35-day study period will be formally tested, provided statistical significance is declared in both of the primary endpoints.

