8.4 Estimands and Intercurrent Events

8.4.1 Primary Efficacy Estimands

The first primary estimand will be the hazard ratio of SNG001 versus placebo for the time to hospital discharge of patients in the ITT population. Intercurrent events will be handled as follows:

Intercurrent event	Policy
Death	Composite variable: Patients who die on or prior to Day 28 will have time to hospital discharge right censored at 28 days (the maximum time to discharge).
Premature treatment discontinuation and missed doses	Treatment policy: The time to hospital discharge will be used regardless of treatment discontinuation and the number of missed doses.
Withdrawal from study following hospital discharge	Treatment policy: The time to hospital discharge will be used regardless of study withdrawal and regardless of the duration of follow-up following hospital discharge. This assumes relapse is independent to the treatment effect.
Withdrawal from study prior to hospital discharge	While-on-study: Time to hospital discharge will be right censored at the time of withdrawal from the study or at 28 days, whichever occurs first. The evaluation period for this endpoint is 28 days, therefore estimating the time to hospital discharge after Day 28 would not be appropriate. Premature study withdrawal is expected to be independent to the treatment effect, therefore a censoring approach in this scenario is considered appropriate. However, this assumption will be tested by appropriate sensitivity analyses.
Other protocol deviations and concomitant medications affecting efficacy	Treatment policy: Time to hospital discharge will be used regardless of any concomitant medication use or protocol deviations.

A tipping point analysis will be performed to implement a treatment policy strategy for patients who withdraw from the study prior to hospital discharge and prior to Day 28 by imputing missing discharge times. The imputation will be repeated by adjusting the likelihood of hospital discharge in each treatment arm independently, to varying degrees. The first primary analysis will be performed on each of the imputed datasets to test the sensitivity to missing data.

A further sensitivity analysis of the first primary estimand will test the missing at random assumption by imputing missing data after study withdrawal through a missing not at random approach.

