## 6 Sample Size

A sample size of 610 subjects in total using a 1:1 randomisation ratio (305 subjects per treatment arm) has been chosen to provide at least 90% power to detect a hazard ratio of 1.45 in time to hospital discharge and a hazard ratio of 1.7 in time to recovery and at least 95% power to declare statistical significance on at least one of the primary endpoints. This sample size has been calculated using a global 2-sided alpha level of 0.05 and adjusting for the Hochberg procedure to allow for multiple comparisons. This sample size also allows for an interim analysis to assess futility after the first 300 randomised subjects (150 subjects per treatment arm) have completed the Day 35 assessment or have withdrawn from the study. The futility analysis is planned to be non-binding.

The power of the study was confirmed via simulation as follows:

Time to recovery and time to discharge in the placebo subjects were drawn from exponential distributions with rate parameters:

$$\text{Placebo Time to Sustained Recovery} \sim \text{Exp}\left(\frac{\log\left(\frac{100}{70}\right)}{28}\right) \text{ and}$$

$$\text{Placebo Time to Sustained Discharge} \sim \text{Exp}\left(\frac{\log\left(\frac{100}{30}\right)}{28}\right)$$

In the simulations, this gives the placebo arm:

- a median time to recovery (50% recovery) of approximately 54.4 days and a 30% recovery at exactly 28 days

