**Table 11: Intercurrent events and policies for the primary estimand of time to recovery**

Intercurrent event	Policy
Death	Composite variable: Patients who die during the study period will have time to recovery right censored at 28 days (the maximum possible time to recovery).
Premature treatment discontinuation and missed doses	Treatment policy: The time to recovery will be used regardless of treatment discontinuation and the number of missed doses.
Withdrawal from study following recovery	Hypothetical: The time to recovery will be used regardless of study withdrawal where recovery was sustained for 7 days Otherwise patients will be censored at the last date known to have limitation of activities for patients who withdrew during the 7 day rebound period. This approach has been proposed because discontinuation during the rebound period is expected to be due to lack of interest/lack of motivation/lack of time to continue participating in the study rather than relapse.

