**Table 23: Secondary estimand definitions**

Endpoint	Population of interest	Consideration of intercurrent events	Summary measure
Proportion of recovered patients at days 7, 14, 21 and 28	ITT	
Composite variable: Subjects who die cannot recover, death after recovery will be considered as a rebound.
 
Treatment policy: Regardless of protocol deviations, treatment adherence and any concomitant therapies received for the treatment of SARS-CoV-2.
 
While on study: Recovery will be determined at study withdrawal, if withdrawal occurs prior to day 35.
	Difference in proportions for each SNG001 arm versus placebo at each day
	Per Protocol	Hypothetical: Estimand for a situation with treatment compliance and no protocol deviations affecting efficacy.	
Proportion of patients discharged from hospital at days 7, 14, 21 and 28	ITT	
Composite variable: Subjects who die cannot be discharged, death after discharge will be considered as a rebound.
 
Treatment policy: Regardless of protocol deviations, treatment adherence and any concomitant therapies received for the treatment of SARS-CoV-2.
 
While on study: Discharge will be determined at study withdrawal, if withdrawal occurs prior to day 35.
	Difference in proportions for each SNG001 arm versus placebo at each day
	Per Protocol	Hypothetical: Estimand for a situation with treatment compliance and no protocol deviations or prior medications affecting efficacy.	
Improvement across the entire OSCI scale at days 7, 14, 21 and 28	ITT	
Composite variable: Death is defined by an OSCI score of 8.
 
Treatment policy: Regardless of protocol deviations, treatment adherence and any concomitant therapies received for the treatment of SARS-CoV-2.
 
While on study: OSCI scores following study withdrawal will be considered missing.
	Odds ratio for each SNG001 arm versus placebo at each day
	Per Protocol	Hypothetical: Estimand for a situation with treatment compliance and no protocol deviations affecting efficacy.	
Change in total BCSS score over the study period	ITT	Treatment policy: Regardless of protocol deviations, treatment adherence and any concomitant therapies received for the treatment of SARS-CoV-2.	Difference in LS means between each SNG001 arm versus placebo

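### Patients who withdraw within 7 days after a recorded discharge or recovery are censored just before it: the censoring depends on the event and departs from the protocol's treatment policy

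*SAP*

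**What the plan says.** **Protocol.** Section 8.4.1 and the synopsis assign treatment policy to withdrawal after discharge: "The time to hospital discharge will be used regardless of study withdrawal and regardless of the duration of follow-up following hospital discharge". Recovery is handled the same way. The protocol states the assumption behind this, namely that relapse is independent of the treatment effect.

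**SAP estimands.** Table 8 relabels the same intercurrent event as hypothetical. Discharge counts if it was sustained for 7 days. If not: "Otherwise, patients will be censored at the last date known to be hospitalised for patients who withdrew during the 7 day rebound period". Table 11 has the matching rule for recovery: "Otherwise patients will be censored at the last date known to have limitation of activities for patients who withdrew during the 7 day rebound period".

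**SAP derivations.** Sections 5.3.1.1 and 5.3.1.2 agree with the tables. Withdrawal inside the 7-day window makes the patient not discharged or not recovered, and the censoring date is the last OSCI score above 2 (discharge) or above 1 (recovery).

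**SAP reason.** Table 8 says "discontinuation during the rebound period is expected to be due to lack of interest/lack" of motivation or time, and not to relapse.

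**SAP changes from protocol.** Section 15 discloses the fixed 7-day window and notes that early withdrawers cannot be assessed for rebound. It does not list the move from treatment policy to a hypothetical strategy.

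**The concern.** The Cox model and the Kaplan-Meier estimator assume that a patient censored on a given day has the same prospects as those still at risk on that day. Here the censored patient is known to have gone home, or to have returned to usual activities, at the next assessment. The recorded discharge or recovery is a condition for this censoring and also fixes its date.

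The stated reason points the other way. If withdrawal in the window reflects lost interest and not relapse, the discharge most likely held, which argues for keeping it. The SAP is also more lenient with other gaps. After discharge, a missing location is taken as not in hospital. For recovery, up to 3 missing assessments are allowed. Withdrawal on day 6 nevertheless voids the event.

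Both primary endpoints are affected, as are the Kaplan-Meier quartiles, the restricted mean and the Day 7, 14, 21 and 28 proportions. The planning simulation in SAP Section 6 lets a patient meet an endpoint and then withdraw, and describes no 7-day confirmation. Its power therefore refers to a slightly different endpoint.

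**Working it through.** **Inputs**
- Sample size (SAP Section 6): "A sample size of 610 subjects in total using a 1:1 randomisation ratio (305 subjects per treatment arm").
- Error rate (SAP Section 6): "This sample size has been calculated using a global 2-sided alpha level of 0.05 and adjusting for the Hochberg procedure".
- Power and effects (Protocol 8.1): "at least 90% power to detect a hazard ratio of 1.45 in time to hospital discharge and a hazard ratio of 1.7 in" the recovery endpoint.
- Placebo at Day 28: 70% discharged and 30% recovered, exponential times.
- Dropout: 25% over 28 days, exponential. Futility stop if both Z statistics are below 1.4 at 300 patients.
- Assumption: q, the share of events followed by withdrawal within 7 days, is not stated. I take the planned dropout hazard as continuing after the event and show a range.

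**1. Reproduce the plan's power.** Per arm, expected events = 305 × λ/(λ+w) × (1 − exp(−28(λ+w))). The hazards are w = ln(100/75)/28 = 0.01027, placebo discharge λ = ln(100/30)/28 = 0.0430 and placebo recovery λ = ln(100/70)/28 = 0.0127.
- Discharge, HR 1.45: 190.8 + 227.6 = 418 events. √(418.4/4) × ln 1.45 = 3.80, and 3.80 − 2.24 = 1.56, so power at alpha 0.025 is 94.0%.
- Recovery, HR 1.7: 80.2 + 122.2 = 202 events, power 93.7%.
- Simulation with Hochberg and the futility rule: 92.4% for both endpoints and 98.6% for at least one.

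The stated power is reproduced with HRs 1.45 and 1.7. The simulation text in SAP Section 6 instead gives 1.7 for discharge and 1.35 for recovery, which yields only about 53% for both. That is a separate matter.

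**2. Share of events lost.** q = 1 − exp(−7 × 0.01027) = 1 − 0.75^(1/4) = 6.9%. SAP Section 6 caps withdrawal at Day 28; with that cap the share is 6.3% to 6.7%.

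**3. Effect on the curves.** Under either rule the patient leaves the risk set at almost the same time; only the event indicator changes. The estimated hazard is therefore λ(1 − q).

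| Placebo discharge | Event counted | q = 6.9% | q = 15% |
|---|---|---|---|
| By Day 28: 1 − 0.3^(1−q) | 70.0% | 67.4% | 64.1% |
| Median: 16.1/(1−q) days | 16.1 | 17.3 | 19.0 |

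The 28-day restricted mean goes from 0.70/0.0430 = 16.3 to 0.674/0.0400 = 16.8 days. The proportion discharged is too low and the time to discharge too long. Placebo recovery by Day 28 moves from 30% to 1 − 0.7^0.931, about 28%.

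**4. Effect on power, q = 6.9% in both arms.** Discharge events fall from 418 to 389 and recovery events from 202 to 188. Power at alpha 0.025 is 92.3% and 91.9%. In simulations of 4,000 to 20,000 trials with independent endpoints, power for both was 92.2% to 92.5% with the event counted and 89.7% to 90.6% under the SAP rule. With withdrawal capped at Day 28 it was 90.3% (Monte Carlo error about 0.2 points).

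**5. Effect on the hazard ratio.** From step 3, apparent HR = true HR × (1 − q_SNG001)/(1 − q_placebo). Cox fits on 600,000 simulated patients agree closely. All unequal rates below are assumptions.

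| q SNG001 / placebo | True 1.45 | True 1.00 | Two-sided rejection when true HR is 1.00 |
|---|---|---|---|
| equal | 1.45 | 1.00 | 5% |
| 10% / 5% | 1.37 | 0.95 | about 8% |
| 5% / 10% | 1.53 | 1.06 | about 8% |
| 15% / 5% | 1.30 | 0.89 | about 18% |
| 5% / 15% | 1.62 | 1.12 | about 18% |

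**The case against.** **Confirmation was not observed.** The SAP event is a discharge or recovery sustained for 7 days, and the protocol endpoint also requires no rebound. What was recorded is unconfirmed, and Section 15 openly explains the 7-day window. This stands: requiring confirmation is defensible, and crediting someone who withdraws a day after discharge assumes no rebound. It does not justify modelling that patient as an average inpatient.

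**The sensitivity analyses may cover it.** A reader might infer that the tipping-point analysis in SAP 9.1.1.3 is useless here. That goes too far. Its sensitivity parameter varies by arm, and at the early-event extreme it places the imputed event next to the censoring day. It cannot single out these patients, though, and it is scoped to withdrawal before the event. The same section also counts a patient as discharged if not readmitted within 7 days. Read literally, that could include early withdrawers, but it does not say so and does not clearly extend to recovery.

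**Table 23.** A reader might see a contradiction in "While on study: Discharge will be determined at study withdrawal, if withdrawal occurs prior to day 35". The text does not say that unconfirmed discharges count, and Section 5.3.1.1 applied at withdrawal gives not discharged. The wording is ambiguous, not clearly inconsistent.

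**Conclusion.** The concern holds and should be fixed. The rule makes censoring depend on the event in both primary analyses, changes the protocol's intercurrent-event strategy without listing that change, and runs against its own rationale. Under the planning assumptions it loses about 6–7% of events per arm. Placebo discharge by Day 28 is about 2.6 points too low, the placebo median about 1.2 days too long, and power for both endpoints about 2 points lower.

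Two stronger conclusions are not supported. First, a reader might infer that the rule creates a false treatment effect. The hazard ratio is biased only if early post-event withdrawal differs by arm, and the documents give no arm-specific rate, so the unequal scenarios show sensitivity only. Second, a reader might infer that the stated 90% power fails. The results fall on both sides of 90%, and with the plan's own cap on withdrawal power for both endpoints is 90.3%.

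The sizes rest on exponential times and on the planned dropout hazard continuing unchanged after discharge or recovery.

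**What to change.** - In SAP Tables 8 and 11 and Sections 5.3.1.1 and 5.3.1.2, return to the protocol's treatment policy. A patient who withdraws inside the 7-day window with no rebound recorded up to withdrawal has the event on the discharge or recovery date.
- Apply the same rule to the Day 7, 14, 21 and 28 discharge and recovery endpoints, and say so in Table 23.
- Keep the present censoring rule as a named sensitivity analysis for both primary endpoints. State how withdrawers are handled in the 7-day discharge analysis of Section 9.1.1.3.
- If the present rule is kept as primary, list the change of strategy in Section 15 and give a rationale consistent with it.

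The cost is SAP wording and one derivation flag; no new data are needed. The price is that rebounds between withdrawal and day 7 go unseen, which the retained sensitivity analysis helps to put in context.
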